7.1.4 Suspected Unexpected Serious Adverse Reaction (SUSAR)

The definition of a SUSAR is any serious adverse event related to an IMP that is both suspected to be related to the IMP and unexpected. In this case the event is not outlined in the SmPC for Aspirin or Vitamin D3.

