7.1.3 Serious Adverse Event (SAE) or Serious Adverse Reaction (SAR)

An SAE fulfils at least one of the following criteria:

- Is fatal results in death
- Is life-threatening

- Requires inpatient hospitalisation or prolongation of existing hospitalisation
- Results in persistent or significant disability/incapacity
- Is a congenital anomaly/birth defect

Since there is no risk arising from the transfer of any PROVENT IMP products via seminal fluid, it has been deemed unnecessary to collect & record pregnancies where the father is a PROVENT study participant.

Serious Adverse Reaction (SAR)

An SAR is an adverse reaction that is classed as serious and which **is consistent with** the information about the medicinal product as set out in the Summary of Product Characteristics (SmPC) for Aspirin or Vitamin D3.

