7.2.2 Causality

The Principal Investigator must assess the causality of all serious adverse events/reactions in relation to the trial treatment according to the definition given. If the SAE is assessed as having a reasonable causal relationship, then it is defined as a SAR.

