7.2.3 Expectedness

The Principal Investigator must assess the expectedness of all SAEs according to the definition given and by referring to the summary of product characteristics (SmPC). If a SAR is unexpected, then it is defined as a SUSAR.

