7.7 Procedures for Reporting Blinded SUSARs

The responsibility for Pharmacovigilance management and reporting is allocated to the CI by the sponsor. Under these circumstances, a dedicated individual(s), with no involvement in data management of the study will be responsible for the un-blinding event. The un-blinding of single cases by the PI/CI in the course of this study will only be performed if necessary for the safety of the trial subject, or if the participant expresses an explicit wish to know the treatment he is or was receiving. See section 5.10.

Any occurrences will be assessed for seriousness, expectedness and causal relationship as if it was the tested IMP that caused the reaction. If the case appears to be a SUSAR it will be un-blinded to the Sponsor and, if the administered product is the tested IMP, the case will be reported by the sponsor as a SUSAR to the MHRA, the Main Research Ethics Committee and the IMP provider by Barts CTU within the timelines outlined in section 7.4.2. The blind will be maintained for the study team, excluding staff involved in data analysis & interpretation,

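### The protocol defines a serious adverse reaction in two incompatible ways, and does not tie expectedness to the SmPC of the suspected drug, so a SUSAR could miss expedited reporting

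*Protocol*

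**What the plan says.** Five places in the protocol govern how a serious event is classified.

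- Section 7.1.3 requires a SAR to agree with "the information about the medicinal product as set out in the Summary of Product Characteristics (SmPC) for Aspirin or Vitamin D3".
- Section 7.1.4 describes a SUSAR as a serious event "both suspected to be related to the IMP and unexpected", and adds: "In this case the event is not outlined in the SmPC for Aspirin or Vitamin D3".
- Section 7.2.2 says the Principal Investigator "must assess the causality of all serious adverse events/reactions in relation to the trial treatment". It continues: "If the SAE is assessed as having a reasonable causal relationship, then it is defined as a SAR".
- Section 7.2.3 requires expectedness to be assessed for all SAEs and states: "If a SAR is unexpected, then it is defined as a SUSAR".
- Section 7.4.1 makes section 4.8 of the aspirin and Vitamin D SmPCs, named together, the reference safety information for the trial.

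The consequence is set in sections 7.7 and 7.4.2. Blinded cases are assessed as though the tested IMP had caused the reaction. "If the case appears to be a SUSAR it will be un-blinded to the Sponsor", and if active product was given the case goes to the MHRA and the ethics committee within 7 days (fatal or life-threatening) or 15 days (other SUSARs).

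**The concern.** There are two separate faults.

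The first is a contradiction. If a SAR must agree with the SmPC, no SAR can be unexpected, and the rule in 7.2.3 has nothing to act on. An investigator cannot follow 7.1.3, 7.2.2 and 7.2.3 together.

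The second is an open rule at the point where it matters. The trial tests two active drugs with different known harms. Section 2.2 itself lists haemorrhagic stroke and gastrointestinal bleeding under aspirin and hypercalcaemia under Vitamin D3. Whether an event is unexpected depends on which SmPC it is held against, and the protocol does not say that this is the SmPC of the drug under suspicion. On the natural reading, one drug's listed harms can make a reaction attributed to the other drug expected.

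What is at stake is the regulatory step that depends on the SUSAR label: unblinding to the sponsor and the expedited report.

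**Working it through.** The plan gives no figure on this point and none is needed. The check is to set the definitions side by side and follow an event through them.

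**Step 1: the two SAR definitions.**

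| Section | Condition for a SAR | Can a SAR be unexpected? |
|---|---|---|
| 7.1.3 | serious, a reaction, and consistent with the SmPC | no |
| 7.2.2 | SAE with a reasonable causal relationship | yes |
| 7.2.3 | presupposes a SAR that may be unexpected | yes, and it is then a SUSAR |

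The first row cannot hold together with the other two.

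**Step 2: does the 7.1.3 wording block the SUSAR route?** No. Section 7.1.4 starts from any serious adverse event related to an IMP, not from a SAR, and 7.2.3 calls for expectedness on every SAE. The contradiction needs correcting, but does not by itself stop a SUSAR from being recognised.

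**Step 3: which list decides expectedness?** Take a serious event with drug A as the only suspect, where A and B are the two active drugs. Compare the natural reading of 7.1.4 with 7.4.1 (unexpected only if in neither SmPC) with a rule that uses the SmPC of the suspected drug.

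| Event listed for | In-neither reading | Suspected-drug rule |
|---|---|---|
| A only | expected | expected |
| A and B | expected | expected |
| neither | SUSAR | SUSAR |
| B only | expected | SUSAR |

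The readings differ in one row: a reaction suspected to come from one drug and listed only for the other. If both drugs are suspected and only one lists the event, the in-neither reading again gives expected. A rule that treats a case as a possible SUSAR when any suspected drug does not list the event would flag it.

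**Step 4: what follows from the label?** In the differing row the case does not appear to be a SUSAR. It therefore does not trigger the unblinding in 7.7, and the 7- or 15-day reporting in 7.4.2 does not apply. Section 7.4.1 sets day zero for the MHRA at notification of a medically assessed SUSAR, so no clock starts.

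**Step 5: what still happens?** Under 7.4.1 the event goes to the trials unit within 24 hours and to the sponsor within 1 working day. The chief investigator or a delegate reviews every SAE, confirms expectedness and relatedness, and may upgrade after agreement with the Principal Investigator. Under 7.6 it enters the annual safety report to the MHRA, the ethics committee and the suppliers. Under 8.3 and 10.0 the DMC reviews toxicity at least six-monthly and sees unblinded comparisons by arm.

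**The case against.** The strongest reply is that pooling of the two SmPCs is nowhere stated as a rule. Section 7.1.4 speaks of a single IMP, 7.1.3 of a single medicinal product and 7.7 of a single tested IMP. Section 7.1.2 defines an adverse reaction as a response to one IMP. The phrase naming the two SmPCs could mean whichever applies. This stands in part: the text permits a drug-by-drug reading. But the singular terms do not say which of two active drugs is meant, 7.2.2 refers causality to the trial treatment as a whole, and no section instructs the assessor to match the list to the suspect.

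The second reply is that several safeguards remain, as in step 5 above. This also stands, and it limits the consequence. A reader might infer that such a reaction would never be unblinded or reported; the protocol does not support that. The safeguards do not close the gap, however. The chief investigator judges expectedness against the same joint reference information, and an annual report does not replace an expedited one.

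The third reply concerns illustrations that come easily to mind: a serious bleed in a man on Vitamin D3 and placebo aspirin, or hypercalcaemia in a man on aspirin and placebo oil. A blinded assessor would naturally suspect aspirin in the first case and Vitamin D3 in the second, and would find the event expected under any sensible rule unless the other drug was also suspected. These cases show ordinary blinded handling and not the defect.

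**Conclusion.** The point holds in a limited form. Sections 7.1.3, 7.2.2 and 7.2.3 contradict each other as written; this rests on no assumption. The second part rests on the natural reading of 7.1.4 with 7.4.1, which the text permits and never excludes. On that reading, a serious reaction suspected to come from one drug but listed only for the other can lose SUSAR unblinding and the expedited report. It does not lose SAE reporting, chief investigator review, the annual safety report or DMC review.

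The documents allow no estimate of how often this would happen. It is tempting to count men on exactly one active drug: with 17 per arm, 2 × 17 = 34 on aspirin only plus 17 on Vitamin D3 only gives 51 of 102. That describes allocation. Classification is made blind and turns on the drug suspected, so the misclassification could equally arise in the 34 men on both drugs. The count is neither an estimate nor a bound. In a study of 102 men the number of such cases is likely to be small. The correction should be made because the definitions cannot all be followed and they decide a reporting duty.

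**What to change.** - In 7.1.3, define a SAR by seriousness and causality alone, whether or not it is expected, so that it agrees with 7.2.2 and 7.2.3.
- In 7.1.4, 7.2.2, 7.2.3 and 7.4.1, state that causality and expectedness are assessed separately for each IMP, against that IMP's own SmPC.
- State that a case is treated as a possible SUSAR, for the purposes of 7.7, if the event is unlisted for any IMP suspected of causing it.

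The cost is a few sentences of definition and one further causality and expectedness line on the SAE eCRF. The only downside is an occasional extra unblinding, done by the dedicated individual whom 7.7 already provides for outside data management.

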7.2 Investigator's Assessment

7.2.1 Seriousness

The Principal Investigator responsible for the care of the patient, or, in his absence, an authorised doctor within the research team, as specified on the site delegation log, is responsible for assessing whether the event is serious according to the definitions given in section 7.1.

7.2.2 Causality

The Principal Investigator must assess the causality of all serious adverse events/reactions in relation to the trial treatment according to the definition given. If the SAE is assessed as having a reasonable causal relationship, then it is defined as a SAR.

7.2.3 Expectedness

The Principal Investigator must assess the expectedness of all SAEs according to the definition given and by referring to the summary of product characteristics (SmPC). If a SAR is unexpected, then it is defined as a SUSAR.

7.2.4 Severity

The Principal Investigator must assess the severity of the event according to the following terms and assessments. The intensity of an event should not be confused with the term "serious" which is a regulatory definition based on patient/event outcome criteria.

Mild: Some discomfort noted but without disruption of daily life **Moderate:** Discomfort enough to affect/reduce normal activity

Severe: Complete inability to perform daily activities and lead a normal life

7.3 Notification and reporting of Adverse Events or Reactions

If the AE is not defined as serious, the participant is followed up by the research team. The AE is documented in the participants' medical notes (where appropriate) and the CRF. (See Appendix 2 for Flowchart for Safety Reporting)

7.4 Notification and Reporting of Serious Adverse Events and SUSARs

7.4.1 Serious Adverse Events (SAEs)

SAEs must be reported to Barts CTU, acting on behalf of the sponsor, within 24 hours of the PI or research team becoming aware of the event (this delegation is documented in the 'Conditions of Sponsorship Agreement'). They should also be recorded in the subjects' notes and the relevant eCRF.

The Barts CTU will forward the SAE to the sponsor within 1 working day of receipt. Day zero for reporting to the MHRA is the day that the Barts CTU is notified of a medically assessed SUSAR.

The initial report must be made by completing a SAE eCRF accessible via the PROVENT web application. In addition the SAE eCRF must be signed electronically within the web application by the PI or delegate. If for any reason the web application cannot be accessed, a paper SAE CRF should be completed and faxed to the following number;

Reporting SAEs to Barts CTU/Sponsor

Web app: https://www.cptu-edc.org

[contact]

Nominated co-investigators will be authorised to sign the SAE forms in the absence of the CI at the coordinating site, or nominated Sub-investigators in the absence of the PI at the participating sites. The report should be as complete as possible, including details of the current illness and the serious AE, the reason why the event was considered serious, date of onset and stop date (if applicable), diagnostic procedures and treatment of the event, relevant medical history and concomitant medication and action taken with the IMP (if applicable).

The Barts CTU will identify any missing information for each reported SAE. Requests for follow up will be sent for further processing to the investigator. Follow up information will be required at regular intervals from the investigators until all queries are resolved or no further information can be reasonably expected. Following this, the PROVENT CI (or delegate) will review all SAEs. The CI (or delegate) will confirm expectedness and relatedness. He/She has the right to upgrade if judged to be necessary, but only once discussed and agreed with the PI. A record of this discussion should be made in the participant's medical notes, and within the notes section of the relevant eCRF.

The original and any subsequent follow up of Serious Adverse Event CRFs will be recorded in the PROVENT web application. The local sites should keep all signed copies of SAE reports within their IF.

Whilst the IMPs in this study are expected to be well tolerated, the contents of Section 4.8 'Undesirable Effects' in the SmPCs for aspirin & Vitamin D will act as the RSI for the trial. The SmPC with current regulatory approval for the trial will be used to assess SAE reports to identify SUSARs.

Expected Non-Reportable SAEs

In the event of planned hospitalisations, this will be noted in the patient's notes and CRFs but will not be reported as a SAE. Similarly, progression of prostate cancer will not be reported as a SAE as this is an expected outcome for patients in this study but it will be recorded within the application. . Should the patient be withdrawn from the study for disease progression, an End of Study CRF will be completed.

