7.1.2 Adverse Reaction (AR)

An AR is any untoward and unintended response in a subject to an Investigational Medicinal Product (IMP), which is related to any dose administered to that subject. All adverse events judged by either the reporting investigator or the Sponsor as having a reasonable causal relationship to a medicinal product qualify as adverse reactions. The expression reasonable causal relationship means to convey in general that there is evidence or argument to suggest a causal relationship.

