7.8 Overview of the Safety Reporting Process/Pharmacovigilance Responsibilities

The CI has the overall pharmacovigilance responsibility. The CI has a duty to ensure that Pharmacovigilance monitoring and reporting is conducted in accordance with the sponsor's requirements.

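### Section 7.4.1 lets the Chief Investigator upgrade an SAE to related only if the site investigator agrees, whereas section 7.1.2 makes either party's judgement sufficient

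*Protocol*

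**What the plan says.** Three sets of provisions in the protocol bear on this.

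- **Who can make an event a reaction.** Section 7.1.2 says that events "judged by either the reporting investigator or the Sponsor as having a reasonable causal relationship to a medicinal product qualify as adverse reactions". One of the two parties is enough.
- **Who assesses and who reviews.** Section 7.2.2 starts with the site: "The Principal Investigator must assess the causality of all serious adverse events/reactions in relation to the trial treatment according to the definition given". Section 7.2.3 gives the PI expectedness as well, and defines an unexpected serious reaction as a SUSAR. Section 7.4.1 then adds a central review: "The CI (or delegate) will confirm expectedness and relatedness". The next sentence limits that review: "He/She has the right to upgrade if judged to be necessary, but only once discussed and agreed with the PI".
- **Who acts for the sponsor.** Section 7.7 states: "The responsibility for Pharmacovigilance management and reporting is allocated to the CI by the sponsor". Section 7.8 adds: "The CI has the overall pharmacovigilance responsibility".

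On timing, section 7.4.1 fixes the start of the regulatory clock: "Day zero for reporting to the MHRA is the day that the Barts CTU is notified of a medically assessed SUSAR". Section 7.4.2 gives 7 days for fatal or life-threatening SUSARs and 15 days for the others.

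**The concern.** The CI's review in 7.4.1 is the only sponsor-side causality review of all SAEs that the protocol describes. If that review can raise an event to related only with the site's consent, the site's opinion prevails whenever the two disagree in that direction. The definition in 7.1.2 exists so that one party's suspicion is sufficient.

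What is at stake is the classification and timing of expedited safety reports in a multi-site, double-blind drug trial. A SUSAR must first be a suspected reaction. An event held at unrelated therefore never reaches the question of expedited reporting, however unexpected it is. Staff who follow 7.4.1 to the letter would be complying with the protocol while departing from its own definition of a reaction.

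**Working it through.** No figure is involved, so the check compares the two sections as decision rules.

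**Rules**

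- Section 7.1.2: reaction = (investigator judges related) OR (sponsor judges related).
- Section 7.4.1: upgrade at central review = (CI judges that it should be upgraded) AND (PI agrees).
- Link between them: sections 7.7 and 7.8 place the sponsor's pharmacovigilance management, reporting and overall responsibility with the CI.

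**Outcomes for relatedness**

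1. PI says related. Reaction under both rules.
2. PI says unrelated, CI/sponsor says unrelated. Not a reaction under either rule.
3. PI says unrelated, CI/sponsor says related, PI then agrees. Reaction under both rules.
4. PI says unrelated, CI/sponsor says related, PI does not agree. Reaction under 7.1.2; unrelated SAE under 7.4.1.

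The rules conflict in case 4 only.

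**What follows in case 4.** Suppose the event is also unexpected. Under 7.1.2 and 7.1.4 it is a suspected unexpected serious reaction. Under 7.4.1 it has not been upgraded, so nobody has notified the trials unit of a medically assessed SUSAR, and day zero has not occurred. In 7.4.1 the CI's review is placed after the follow-up queries on the SAE have been settled or exhausted, and discussion with the PI comes later still. A period with no running clock is therefore possible even when the PI eventually agrees (case 3).

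**Do other sections resolve case 4?**

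- The trials unit forwards each SAE to the sponsor within one working day (7.4.1). This informs the sponsor but gives it no stated route to override the site.
- Section 7.4.2 provides for joint review by the CI and sponsor, but describes it for events already entered as SUSARs. The SUSAR questions are completed by the PI or a co-investigator, and the form is signed by the PI or delegate, so the site also controls that entry point.
- Section 7.7 provides for unblinding to the sponsor, and for reporting if the product is active, when a case looks like a SUSAR. It does not say whose view decides that.

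**Expectedness.** The agreement condition in 7.4.1 follows directly on a sentence that covers both expectedness and relatedness, so it applies to both. Section 7.1.2 is about causality alone. For expectedness, the condition is a parallel weakness and not a contradiction of 7.1.2.

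**The case against.** The strongest reply is that 7.1.2 names the sponsor, not the CI. The protocol often treats them as separate parties: the sponsor is the university, it receives every SAE, and 7.4.2 has it review SUSARs alongside the CI. The clause in 7.4.1 binds only the CI or delegate, so the sponsor could in principle form its own causality view under 7.1.2. Section 7.7 can be read the same way, since its trigger mentions no agreement by the PI. This stands in part: the protocol never says outright that the sponsor's own view may be blocked. But it describes no separate sponsor assessment of SAEs that the PI has called unrelated, and 7.7 and 7.8 assign that function to the CI. The conflict remains for anyone working from the text.

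A second reply is that disagreement may be handled elsewhere. The flowchart in Appendix 2 is not reproduced in the text reviewed, and section 9.2 lists a separate SAE reporting plan. Either might contain a tie-break, but the wording in 7.4.1 would still contradict 7.1.2.

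Several stronger readings are tempting and are not supported.

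- **That the veto distorts the decision to proceed to the main trial.** A disputed event is still recorded as an SAE and sent to the sponsor, and the Data Monitoring Committee sees unblinded data by arm (section 10.0). The criterion in sections 2.3 and 8.1 is minimal adverse effects in any arm, not a count of attributed reactions.
- **That the 7- and 15-day limits would be breached.** Under 7.4.1 they have not begun to run in case 4. What can be said is that a report may be absent, or later than the sponsor-side suspicion.
- **That the CI may freely downgrade a site's judgement.** Section 7.4.1 grants a right to upgrade and mentions no right to downgrade.

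**Conclusion.** The concern holds for relatedness. Sections 7.1.2 and 7.4.1 give opposite classifications when the PI says unrelated, the CI or sponsor says related, and the PI does not agree. An event of that kind that is also unexpected can be left out of SUSAR reporting, or reach it late, by someone following 7.4.1 as written. For expectedness, the agreement condition is a weakness worth removing at the same time.

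The size is one case out of four in the decision table. The protocol gives no expected number of SAEs or rate of disagreement, so no frequency can be attached; events of this kind are likely to be few. The conclusion rests on two readings: that the right to upgrade refers to the expectedness and relatedness named in the preceding sentence, and that the CI acts for the sponsor in this review, as 7.7 and 7.8 indicate. The correction should be made because it concerns participant safety reporting and costs almost nothing.

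**What to change.** In section 7.4.1, replace the condition requiring the PI's agreement with wording to this effect: the CI or delegate discusses a proposed upgrade with the PI but does not need the PI's agreement; the event is handled as related if either the PI or the CI/sponsor judges it so; and both opinions are recorded. Removing the condition also frees upgrades of expectedness from it.

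In section 7.4.2, align the completion and sign-off of the SUSAR form so that an upgrade by the CI or sponsor can be reported without the PI's agreement. Check that the Appendix 2 flowchart and the SAE reporting plan follow the same rule.

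Reconciling the sections does not require a new definition of day zero or a rule on downgrading.

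The cost is a few sentences in two sections and at most a few more expedited reports.
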